- Significant safety issues that are likely to (or have the potential to) affect to a significant degree the safety or rights of participants or the reliability and robustness of the data generated in the clinical trial.
- Urgent safety measures are implemented to remove or prevent a significant safety issue.
- Safety reports relating to the clinical trial's continuation, suspension, or discontinuation for safety reasons.
- Non-compliance with the protocol, SOPs, GCP, and applicable regulatory requirement(s) significantly affects or has the potential to affect human subject protection or reliability of trial results significantly.
- Participant complaints or concerns were received concerning the conduct of the research.
- Significant modifications to the clinical trial that is likely to affect to a significant degree the safety or rights of participants or the reliability and robustness of the data generated in the clinical trial.
- Addition of participating trial sites, contractual arrangements at participating sites or modifications to legal agreements.
- The intention is to conduct the trial in other countries.

4. Trial Objectives and Purpose

This project aims to characterise the effect and time course of topical anti-allergy treatments on ocular surface dendritic cell density, morphology, and topographical distribution, and the relationships with changes in signs and symptoms of allergic conjunctivitis.

The research question that this study seeks to address is:

Do different therapeutic topical eyedrops (e.g., combination antihistamines and mast cell stabilisers versus corticosteroids) have different effects and time course on ocular surface dendritic cell density, morphology, and topographical distribution in allergic conjunctivitis patients?

The primary endpoint of the trial is the change in dendritic cell density (measured by counting their average number in a given area manually) using in-vivo confocal microscopy.

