After taking history, participants will be asked to complete questionnaires (eligibility phase 1), related to eye and nose allergy symptoms: Numerical Rating Scale (NRS), Mini Rhinoconjunctivitis Quality of Life Questionnaire (Mini-RQLQ), Ocular Surface Disease Index (OSDI), Aston University Allergy Questionnaire (AUAQ), the dry eye questionnaire for the detection of dry eye (Dry Eye Questionnaire: DEQ-5) and the Eye Allergy Patient Impact Questionnaire (EAPIQ). Changes in symptoms during the treatment will be recorded using a Numerical Rating Scale (NRS). Changes in symptoms and signs will be recorded, reported and analysed from both eyes as appropriate. Each questionnaire includes detailed instructions on how to complete them. To confirm participants' allergy status, a Skin Prick Test will be conducted (eligibility phase 2) where a drop of allergen will be placed on the forearm, and a slight skin prick will be made using a lancet at the same spot to allow the allergen to be absorbed by the skin. Ten minutes later, the skin's allergic reaction will be determined by measuring the size of the hive formed on the skin. Visual acuity, Tearscope and ocular surface health integrity with white light slit lamp biomicroscopy will follow. Ocular staining will be performed before and after each time taking confocal microscopy images.

Ocular surface dendritic cell images will be taken using the *in vivo* confocal microscopy (IVCM) at the baseline visits and at each follow-up visit. A topical anaesthetic eyedrops will be applied to the examined eye of the participants (right eye) and a soft lubricating gel will be applied over the microscope probe to avoid any discomfort. Participants will be directed to look at a single white fixation light with the contralateral eye to help maintain head posture and eye position. A gentle touch by the IVCM probe will be apply on the corneal surface (the transparent front part of the eye) to capture multiple images from different locations on the cornea.

After the baseline visit, participants will be randomly given either treatment or control eyedrops and instructed to put one drop in each eye, twice daily for two weeks. Participants will be asked to visit the clinic at different interval periods including 24 hours, 7 days and 14 days during the treatment period, and post-treatment at days 21 and 28, to repeat all the examinations except the Skin Prick Test (Table 1).

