- SPSS software (version 28.0; SPSS inc.) will be used. Differences in symptoms and signs between treatment groups and the control group will be assessed using the Independent Sample t-test or Mann-Whitney U test, as appropriate. For dendritic cell density, A linear mixed model with effect for individuals will be used to examine differences in (log) dendritic cell density between groups and between corneal and conjunctival locations. Pairwise comparisons between groups and locations will be obtained within the model. P-values for multiple comparisons between locations will be adjusted by Holm's step-down Bonferroni method.
- Mann-Whitney U test (for cell body size) and Fisher's Exact test (for the presence of dendrites) will be used to assess differences in dendritic cell morphology between groups. Friedman, and Wilcoxon Signed Ranked Test (for cell body size) and Cochran's Q Test (for the presence of dendrites) will be used to assess differences in dendritic cell morphology across locations and the p-values for pairwise comparison between locations were adjusted by Holm's step-down Bonferroni method.
- Associations between dendritic cell and ocular surface symptoms and signs will be assessed using a univariate Spearman's correlation coefficient (for dendritic cell density and cell body size) and Mann-Whitney U test (for the presence of dendrites).

19. Data Handling, Ownership and Access

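### The stated density analysis compares levels of log density between groups and locations, and so does not address the primary endpoint (change) or the time course

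*Protocol*

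**What the plan says.** Section 4 of the protocol sets the target. "The primary endpoint of the trial is the change in dendritic cell density", measured by in-vivo confocal microscopy. The project aims to "characterise the effect and time course of topical anti-allergy treatments on ocular surface dendritic cell density", and the research question is whether the treatments "have different effects and time course on ocular surface dendritic cell density".

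Section 14 schedules images at baseline and then at "24 hours, 7 days and 14 days during the treatment period, and post-treatment at days 21 and 28". Table 1 agrees: confocal microscopy is marked at six visits, Visits 2 to 7.

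Section 18 gives the density analysis: "A linear mixed model with effect for individuals will be used to examine differences in (log) dendritic cell density between groups". In full, the comparison is of "differences in (log) dendritic cell density between groups and between corneal and conjunctival locations". It continues: "Pairwise comparisons between groups and locations will be obtained within the model", and "P-values for multiple comparisons between locations will be adjusted by Holm's step-down Bonferroni method". This is all the protocol says about analysing group differences in density. The only other mention of density is a correlation with symptoms and signs.

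**The concern.** The endpoint is a change and the question concerns its course over time, but the outcome named in Section 18 is a level and the named contrasts are group and location. A statistician following Section 18 would have no instruction for estimating change from baseline, no visit at which to compare the groups, and no interaction to describe the time course.

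Two things are at stake. First, if all visits were put into one model with no time term, the group contrast would average one pre-treatment, three on-treatment and two post-treatment measurements. Second, with no primary visit named, there are five follow-up visits from which to choose once data are seen, and the only multiplicity adjustment stated for density covers locations.

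**Working it through.** **No figure in the plan decides this point.** The nearest is the 25 per arm in Section 8. With an effect size of 0.512, alpha 0.05 and power 0.80, a one-sided paired or one-sample t-test needs exactly 25 (power 0.800), whereas a two-sided independent-samples t-test needs 61 per arm. Section 8 does not name its test, so this does not show which density analysis was intended.

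**Endpoint and analysis side by side**

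| Element | Sections 4 and 14 | Section 18 |
|---|---|---|
| Outcome | Change in density | Level of (log) density |
| Time | Time course; baseline plus five follow-ups | Not mentioned |
| Baseline | Imaged | Not mentioned |
| Contrasts | Treatment differences in effect and time course | Groups; locations |
| Multiplicity | – | Holm, between locations |

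The other tests in Section 18 do not fill the gap. The related-samples tests for morphology (Friedman, Wilcoxon signed-rank, Cochran's Q) are assigned to locations, not visits.

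**Dilution, if all six visits are pooled with no time term.** The pooled group contrast is the mean of the effect over baseline, 24 hours and days 7, 14, 21 and 28. The protocol gives no time profile, so the profiles below are assumptions, with the peak set to 1:

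- Immediate and lasting: (0+1+1+1+1+1)/6 = 5/6 = 83%.
- Half-size at 24 hours and day 21, absent at day 28: (0+0.5+1+1+0.5+0)/6 = 3/6 = 50%.
- Present only at days 7 and 14: (0+0+1+1+0+0)/6 = 2/6 = 33%.

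**Gain from baseline adjustment.** Residual variance is multiplied by 1 − ρ², where ρ is the correlation between baseline and follow-up (assumed 0.5 to 0.7). At 0.5, 1 − 0.25 = 0.75 remains, a cut of 25%. At 0.7, 1 − 0.49 = 0.51 remains, a cut of 49%.

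**Illustrative power.** Assumptions: 25 per arm, two arms compared at one location, two-sided 0.05, day-14 effect 0.8 SD, equal correlation r between visits, normal approximation. Power = Φ(effect/SE − 1.96) and SE² = (2/25)·v. For the six-visit mean, v = (1+5r)/6; for baseline-adjusted day 14, v = 1 − r². The rise-and-fall profile is (0, 0.25, 0.75, 1, 0.5, 0.25), mean 2.75/6 = 0.458, so the pooled effect is 0.458 × 0.8 = 0.367. For the immediate and lasting profile it is 5/6 × 0.8 = 0.667.

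Example at r = 0.3, rise and fall: v = 2.5/6 = 0.417, SE = √(0.08 × 0.417) = 0.183, and power = Φ(0.367/0.183 − 1.96) ≈ 0.52.

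| Contrast | r = 0.3 | r = 0.5 | r = 0.7 |
|---|---|---|---|
| Pooled, rise and fall | 0.519 | 0.396 | 0.322 |
| Pooled, immediate and lasting | 0.955 | 0.870 | 0.777 |
| Day 14, baseline-adjusted | 0.843 | 0.904 | 0.977 |

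Pooling is costly when the effect rises and falls. If the effect is immediate and lasting and r is low, pooling can have more power than a single visit, because it averages more measurements. It still gives neither a change nor a time course.

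**The case against.** The strongest reply is that silence is being read as exclusion. Section 18 describes comparisons and does not list the model's fixed effects. The statistical analysis plan is not at hand, and covariates and repeated-measures structure commonly belong there. Section 18 is also compatible with fitting the model at each visit, or to change scores, and in those cases there is no dilution.

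Much of this stands, and it limits what may be concluded:

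- A reader might infer that the model certainly has no visit or baseline term. The protocol does not say so; the absence is read from the comparisons it names.
- A reader might infer that following the plan must give a diluted estimate. That needs all six visits pooled without a time term, which the protocol does not state. The effect profiles are assumed. Section 5 reports falls in density after two weeks, one month, and 3 and 6 months of treatment in vernal disease, which does not establish a profile here.
- A reader might infer bias from not adjusting for baseline. Allocation is randomised, so a comparison at one pre-named post-baseline visit would be valid without adjustment; adjusting adds precision. No such visit is named.
- A reader might infer that zero counts would be lost on taking logs. The protocol neither says how often zeros occur nor that they are dropped, and their handling is ordinary detail for the analysis plan.

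What does not stand is that the whole point can be left to the analysis plan. The protocol has already named an outcome and a set of contrasts, and they do not match its own primary endpoint. An analysis plan that tested change at a named visit would have to supply a different primary contrast, not merely elaborate this one.

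**Conclusion.** The point holds as a mismatch within the protocol: the endpoint is change and the question is time course, while the stated density analysis concerns levels, with contrasts only between groups and locations. No other section brings visit, baseline or change into the analysis. This conclusion needs no numerical assumption.

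The numbers are conditional. Retention of 83%, 50% or 33% of the peak effect applies only under six-visit pooling with the assumed profiles, and the 25% to 49% variance reduction only for a correlation of 0.5 to 0.7. They show what the ambiguity could cost, not what the trial will lose. Because the mismatch concerns the primary endpoint, it should be settled before unblinding.

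**What to change.** Amend Section 18 as follows:

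- Model post-baseline log density on baseline log density at the same location, group, visit, group-by-visit, location and group-by-location, with a participant random effect and correlation over visits.
- Name in advance one primary visit (for example day 14, the end of treatment), one primary location (Section 8 bases the sample size on the central cornea) and which of the three pairwise group comparisons is or are primary. The visit and location shown are suggestions; the sponsor must choose and state them.
- Report the other follow-up visits from the same model as the time course.

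Without a three-way term this model assumes that the group-by-visit pattern is the same at every location. The sponsor should either accept that explicitly or add the term.

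The cost is a protocol amendment and a somewhat more complex model, with correlation over visits and locations to specify for about 75 completers. It can be fitted in the software already named and needs no new data.

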The secondary endpoints are the change in dendritic cell morphology (determined by measuring cell body size and presence of dendrites manually), using in-vivo confocal microscopy, and the change in eye allergy symptoms (including itchy eyes or watery eyes or burning feeling or feeling like there is dirt or grit in your eyes) and the change in eye allergy signs (including redness or conjunctival chemosis or conjunctival papillae or conjunctival follicles) and the possible relationship between ocular immune system and eye allergy clinical symptoms and signs.

5. Background Information

Allergic conjunctivitis is a group of diseases, that is usually bilateral and caused by the ocular response to various environmental and chemical air pollution allergens. The prevalence of allergic diseases has increased globally in the past few decades, and almost 1 in 5 Australians (19.6% of the total population) report some form of allergy [1-4]. The prevalence of ocular allergy is increasing worldwide, affecting individuals' quality of life, and causing a significant socioeconomic burden [5-8]. In a recent epidemiological survey of allergy prevalence in the US, 15 - 40% of the population reported having at least one ocular allergy symptom and were classified to have allergic conjunctivitis [9]. Allergic conjunctivitis can be managed using a range of options beginning with allergen avoidance and progressing to more complex treatments, including topical pharmacological agents such as decongestants, antihistamines, mast cell stabilisers, corticosteroids, non-steroidal anti-inflammatory drugs, and immunosuppressive agents [10-17].

Ocular dendritic cell play a substantial role in initiating the immune response in the setting of ocular allergies by capturing and processing antigens in peripheral tissue and migrating from the affected tissue to the lymph nodes via lymphatic vessels [18]. Once inflammation occurs, the phenotype of dendritic cell undergoes rapid change, antigen-capturing capability declines, and T-cell stimulation function increases [19]. However, the changes in ocular surface dendritic cell density and morphology were not associated with changes in ocular allergy symptoms or signs in the milder and severe forms of ocular allergy [20-21].

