In a recently published article, dendritic cell density was higher in participants with allergic conjunctivitis at the corneal centre, corneal periphery, limbus, and conjunctiva but not at the inferior whorl, compared to controls [21]. Dendritic cell density was highest at the limbus followed by the corneal periphery and the lowest density was at the conjunctiva, and there was no difference between the corneal centre and the inferior whorl [21]. Dendritic cell morphology assessment was based on cell body size (small, medium, large), and the presence of any dendrites, the presence of long dendrites, and the presence of thick dendrites [21]. At corneal centre, dendritic cell had a larger cell body size, and there was a higher percentage of dendritic

cell with dendrites and with long dendrites in the allergic conjunctivitis group [21]. Cell body size, the presence of long dendrites and the presence of thick dendrites were not significantly different between groups at other locations [21]. When allergic participants were symptom free, corneal dendritic cell body size was smaller and there were fewer dendritic cell with long dendrites [22]. At the bulbar conjunctiva, dendritic cell density was reduced during the symptom-free phase but did not change in morphology [22].

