The Perkins tonometer is a handheld applanation model used to measure intraocular pressure. The principle of applanation tonometry is based on the force required to flatten a certain area of the spherical surface of the cornea is the same as the pressure inside the eye. The Perkins tonometer is a very popular handheld applanation tonometer used in humans.

- **The Oculus Keratograph 5M (K5)**

This is an advanced corneal topographer with a built-in real keratometer and a colour camera optimized for external imaging. In our study the tear film break-up time will be measured automatically and non-invasively.

- **Slit lamp biomicroscopy**

The ocular surface and anterior segment will be examined using a slit lamp biomicroscope and ocular surface signs, including conjunctival and limbal redness (graded using the Cornea and Contact Lens Research Unit (CCLRU) grading scale), conjunctival chemosis, papillae and follicles (graded using the Japanese grading scale for allergic conjunctivitis [8]).

- **Ocular staining**

A wetted fluorescein strip (harmless yellow dye) and a wetted lissamine green strip (harmless green dye) will be then gently touched to the fornix of the lower lid. Participants will be asked to blink continuously to enable the smooth spreading of the stain over the eye, allowing for the evaluation of any surface defects. Ocular surface (corneal and conjunctival) staining will be assessed using the Oxford grading scale [9]. These dyes are routinely used in optometry practices worldwide and are safe to use.

- **Confocal microscopy**

A confocal microscope will be used to visualise the corneal sub-basal corneal nerves and dendritic cell in vivo. A probe that emits harmless laser light will come in contact with the transparent front part of the eye for approximately 5 minutes, and microscopic images of the cornea will be captured. Images will be captured from the right eye only. To avoid any discomfort to the patient or causing abrasions on the transparent surface of the eye a topical anaesthetic will be installed in the tested eye and a soft lubricating gel will be applied over the microscope probe.

All the above-mentioned clinical procedures (except the Skin Prick Test) will be repeated for the eligible participants at the follow-up visits.

Reference list

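### Cochran's Q on presence of dendrites has no cell denominator, so a difference in cell number between locations can be reported as a difference in cell morphology

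*Protocol*

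**What the plan says.** Section 4 of the protocol makes density the primary outcome: "The primary endpoint of the trial is the change in dendritic cell density". Morphology is a secondary endpoint, "determined by measuring cell body size and presence of dendrites manually". No cell denominator is attached to the dendrite part.

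Section 18 then fixes three uses of the dendrite variable:

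- Across locations: "Cochran's Q Test (for the presence of dendrites) will be used to assess differences in dendritic cell morphology across locations", with Holm-adjusted pairwise comparisons.
- Between arms: "Fisher's Exact test (for the presence of dendrites) will be used to assess differences in dendritic cell morphology between groups". The unit, participant or cell, is not given.
- Against symptoms and signs: "Mann-Whitney U test (for the presence of dendrites"), which splits the sample in two on that variable.

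Section 5 reports from the cited earlier study that "Dendritic cell density was highest at the limbus followed by the corneal periphery and the lowest density was at the conjunctiva". For the corneal centre in allergic participants it reports that "there was a higher percentage of dendritic" cells with dendrites, which is a measure with cells as the denominator. Section 10 says "Images will be captured from the right eye only", so each participant contributes one eye.

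**The concern.** Cochran's Q compares matched binary responses. Cells at the limbus cannot be matched to cells at the conjunctiva, so the matched unit has to be the participant and each location has to be reduced to one yes or no. The Mann-Whitney split against symptoms and signs fits the same reduction. If presence means that at least one imaged cell has dendrites, a location with more cells has more chances to score yes.

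The test is described as a test of morphology, but under that coding it responds to cell number and morphology together. The protocol itself says that cell number differs by location, and topographical distribution is part of the trial's aim. The stake is that a known density gradient is reported as a finding about cell shape, on a named secondary endpoint.

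**Working it through.** The protocol gives no figure for these tests, so there is none to reproduce.

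**Inputs from the protocol.** 75 completers, 25 per arm, alpha 0.05 (Section 8); density differing by location (Section 5).

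**Assumptions.** Yes means at least one cell with dendrites. There are five locations, as in the earlier study described in Section 5. The per-cell dendrite probability p is the same everywhere, so no morphology difference exists. Counts are Poisson, with mean m for the location multiplied by a gamma participant factor (shape 2, mean 1). The protocol gives no cell counts, so a range is shown.

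**Mechanism.** With n cells, P(yes) = 1 - (1-p)^n. Averaged over the count model, P(yes) = 1 - (1 + pm/2)^-2. At p = 0.4:

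- m = 1: 1 - 1.2^-2 = 0.31
- m = 2: 1 - 1.4^-2 = 0.49
- m = 4: 1 - 1.8^-2 = 0.69
- m = 8: 1 - 2.6^-2 = 0.85
- m = 30: 1 - 7^-2 = 0.98
- m = 80: 1 - 17^-2 = 0.997

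P(yes) runs from 0.31 to 0.85 between 1 and 8 cells with p fixed. Between 30 and 80 cells it hardly moves.

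**Cochran's Q, 75 participants, five locations, p from 0.2 to 0.6.** Share of simulated trials rejecting at 0.05. The first three rows use a within-participant correlation of p of 0.1.

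| Mean cells by location | All participants | Dropping participants with an empty location |
|---|---|---|
| 2/4/2/8/1 | 100% | 70-95% |
| 2/3/2/4/1.5 | 80-96% | 23-45% |
| 10/10/14/20/5 | 91-100% | 63-99% |
| 40/60/40/80/30 | about 3-50% | not tabulated |
| equal at all locations | about 5-7% | not tabulated |

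Repeat runs differ by a few points. Overall the ranges for means of about 1-20 cells are 80-100%, and 24-98% after dropping. Excluding participants with an empty location therefore does not repair the test.

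**Fisher between arms, participant as unit, 25 per arm, same p.** If treatment halves the mean from 4 to 2 cells, P(yes) at p = 0.4 goes from 0.69 to 0.49. Simulated rejection for a two-fold density difference at low counts is about 8-24%. With less spread between participants (gamma shape 4) it was 13-29%, against 0-3% at equal counts. At 50 v 25 cells it is about 0%.

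**Fisher between arms, cell as unit.** With independent cells the rejection rate is 2-6% in every density scenario, so density does not confound it. Cells from one eye are not independent, however. At p = 0.4, 5-10 cells per eye and a within-eye correlation of 0.05-0.3, it rejects about 6-29% of the time with no effect present.

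**The case against.** The strongest reply is that the faulted coding is not written down. Cochran's Q forces a yes/no per location but does not force the any-cell rule, and a statistical analysis plan could define another. That stands as a limit on the claim. It does not remove the problem, because any yes/no per location discards the number of cells behind it. A majority-of-cells rule rejected anywhere from about 4% to 94% of the time when only counts differed, depending on p, the counts and the handling of empty sites. A complete cure replaces the named test, so it changes Section 18 and does not merely add detail to it.

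The second reply is that the fault fades when cells are plentiful. That is correct. At means of 30-80 cells it is modest, and close to absent when p is high.

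The third is that the percentage in Section 5 suggests Fisher's test may be meant for cells. That is a fair reading, and under it Fisher's test is not confounded by density. What is left is the separate fault of clustering within an eye.

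A reader might also infer that density and morphology could not be told apart at all. The documents do not support that. Cell body size is tested separately and is not subject to this mechanism. Density has its own mixed model, so the gradient would be visible beside the dendrite result.

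**Conclusion.** The point holds in conditional form. Cochran's Q on presence of dendrites can reject because cell number differs between locations, with per-cell morphology identical. Under any-cell coding, five locations and 75 participants, it does so in about 80-100% of trials at means of roughly 1-20 cells per location and 3-50% at 30-80, against 5-7% with equal density. All of these counts are assumed.

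It would be too strong to say that the tests always reject when density differs, or that Fisher's test shares the fault in full. Between arms the fault is milder (about 8-24% for a two-fold difference) and needs the participant as unit; the protocol gives no expected between-arm density change.

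The consequence falls on the dendrite half of one secondary endpoint. The primary density analysis is not affected. The change is worth making because the protocol itself documents the density gradient and the repair is cheap.

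**What to change.** In Section 18, replace Cochran's Q and Fisher's test for dendrites with an analysis of cells with dendrites out of cells counted, the same kind of measure as the percentage cited in Section 5.

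- **Model:** binomial with logit link, either a mixed model with random effects for participant and participant-by-location, or a GEE clustered by participant.
- **Terms:** arm, location, visit and arm-by-visit, with the baseline visit in the model. The endpoint is change, so the arm contrasts have to address change from baseline.
- **Location contrasts:** from the same model, Holm-adjusted as now.
- **Empty locations:** a location with no cells contributes no information and is not scored as absent.

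Putting each location's percentage into a rank test is not enough: a Friedman test on the percentage still rejected 5-40% of the time when only counts differed (75 participants). A logistic GEE clustered by participant rejected 6-10% with or without a density gradient (8-9% at equal counts). The remaining excess does not depend on density and is consistent with uncorrected sandwich standard errors, so a small-sample correction is advisable. The mixed model itself was not simulated.

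**Cost:** a wording change, one additional model, and graders recording the number of cells with dendrites beside the cell count. Where cells are few the mixed model may be unstable and need simplifying to a participant random effect only, or to the GEE. Eyes with few cells will contribute little.
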